5.2 Secondary objectives

- Evaluate the safety and tolerability of the SOUNDI system
- Evaluate the level of patient satisfaction in using the SOUNDI system

6. Study population

6.1 Number of patients

The study involves the enrollment of 50 patients belonging to a single Italian centre: Sleep Medicine Center of the Italian Auxological Institute IRCCS - San Luca Hospital in Milan.

To document the patient selection bias, all reasons for non-participation in the study will be recorded on a specific form (Screening Log).

Patients will be identified by a unique alphanumeric code which will be assigned at the time of enrollment based on the center code and enrollment sequence (e.g. Aux-001).

6.2 Inclusion criteria

- Signature of informed consent
- Patients of both sexes, of any ethnicity
- Age between 20 and 70 years
- Prescription, from clinical practice, to carry out a polysomnography on suspicion of a sleep breathing disorder.

6.3 Exclusion criteria

- Women during pregnancy
- Insufficient cooperation/degree of collaboration in following the procedures required by the study
- Participation in another clinical study.
- Allergy to one of the materials in the device
- Pacemaker users.

7. Study procedures

All subjects enrolled in the study will undergo polysomnography (monitoring

nocturnal cardiorespiratory for the diagnosis of apnea in sleep) with traditional polysomnography (Embletta, Natus) according to normal clinical practice and at the same time as data acquisition with the Soundi system.

On the afternoon before the night of the evaluation, at the Sleep Medicine Service clinic, each object will be placed

- a traditional polysomnigraph, as prescribed
- the Soundi experimental device.

The patient will be instructed by the Investigator on the correct management of the devices.

During the visit, the following anthropometric data will be collected: age, Body Mass Index (BMI), neck circumference and abdomen.

Furthermore, the Experimenter will program the devices to begin recording the parameters at the moment the subject expects to recharge and continue for at least 8 consecutive hours.

During the night, at the patient's home, the following parameters will be acquired with two systems: oro-nasal flow, thoracic and abdominal respirations, snoring, ECG, arterial oxygen saturation (SaO₂), body position.

The following morning the subject will return to the clinics to return the two systems which will be detached by the medical staff. There, the subject will be asked to fill out a simple satisfaction questionnaire prepared for the study.

The signals acquired with both systems simultaneously will be processed by the software RemLogic, via automatic analysis software, with subsequent manual correction by a doctor expert in sleep medicine, the following indices used, according to international guidelines, for the diagnosis of respiratory and sleep disorders:

- Apnea Hypopnea Index (AHI) total and supine
- AHI central
- AHI obstructive
- Oxygen Desaturation Index (ODI)
- Average arterial oxygen saturation (SaO₂).
- Minimum SaO₂
- Time with SaO₂ < 90%
- Average heart rate
- Minimum heart rate
- Percentages of time spent in different body positions.

The anthropometric data (age, BMI, neck and abdomen circumference), the parameters deriving from the analysis of the acquisitions of the instrumental polysomnographic signal and the responses to the questionnaire provided by the subject will be reported in the electronic data collection form (CRF).

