2.1 Background

Obstructive Sleep Apnea Syndrome (OSA) is a highly prevalent sleep disorder and is characterized by repeated episodes of obstruction of the upper airways during sleep which are accompanied by intermittent anxiety and sleep fragmentation. OSA, being associated with excessive daytime sleepiness and increased cardiovascular risk, significantly increases mortality and morbidity in the affected population, constituting a public health problem. These consequences are significantly reduced by the early and appropriate implementation of specific treatments for apnea such as Continuous Positive Airway Pressure (CPAP), weight loss, surgery or mandibular advancement systems (MAD).

The diagnosis at the moment is carried out by carrying out polysomnographic tests which can be carried out at home or in a hospital environment. Polysomnography is based on the nocturnal collection of various vital parameters capable of providing an objective quantification of the number, characteristics and intensity of apneas.

The parameters that are acquired during complete polysomnographies are: Electroencephalogram (EEG), eye movements, muscle tone of the mylohyoid muscle and tibial muscles, nasal, thoracic and abdominal respirogram, body position, oximetry, Electrocardiogram (ECG).

For cardiorespiratory polysomnography, the number of parameters is smaller (nasal, thoracic and abdominal respiration, body position, oximetry, ECG).

In both cases, however, the patient must be prepared with the positioning of the sensors in the hours preceding the examination, he must keep them worn throughout the night and have them removed in the morning by expert technicians who also proceed to download the data from the memory on which they are collected during the night. Some tests are carried out at home and therefore the patient must access the hospital in the evening and one in the morning for to dismantle the equipment, or are carried out in the hospital and in this case the patient remains sleeping inside the structure.

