2.2 Rational

To facilitate easier access to the diagnosis and therefore treatment of this pathology with numerous serious repercussions on the health of the individual, various technologically advanced systems are being developed which aim to minimize the bulk of the sensors on the patient, increase the comfort of the examination and reduce the need for multiple hospital visits. Among the recently developed systems is Soundi.

Soundi is a small, lightweight medical device that allows non-invasive monitoring and continuous recording of blood pressure, without the use of a cuff, and a whole series of physiological parameters including temperature, ECG, ejection fraction, blood pressure, respiratory rate, flow, oxygen saturation, apnea/hypopnea index. This innovative device can completely revolutionize the concept of monitors sleep aid, currently carried out using invasive instrumentation methods. Soundi will allow the patient, once worn, to carry out all his normal daily activities without any discomfort.

Simultaneous collection of a number of parameters using a single vital sign detection device can provide close, long-term, low-cost and shareable health status monitoring, with the potential to improve health management and quality of life, promote both early intervention and proactive care and reduce healthcare costs.

The results obtained so far on a population of healthy subjects are very encouraging (2-3-4-5), but its production and introduction on the market as a certified medical device requires its clinical validation on patients.

3. Information about the medical device

Soundi is a wearable medical device for the continuous monitoring of vital parameters capable of collecting useful information for the diagnosis and follow-up of breathing disorders in sleep.

The SOUNDI medical device is produced by the Biocubicasrl company. The measurement unit is made of plastic material (PA12 food grade), the ECG connector cover is made of food grade silicone, ECG cables (Spes Medica SpA) are made of Cu/Ag with PVC insulation and the medical double-sided adhesive (MED6364R) is made up of a double coating, thin, conformable, with transparent and moisture-resistant polyester film on both sides.

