The current prototype of the Soundi device was developed on the basis of a technology patented by Biocubica (Italian patent no. 102016000052588 "Physiological monitoring device" and European patent EP3.248.541 "Physiological monitoring device") (1) and is equipped with the ability to listen, through a particular bell shape, to all the sound evidence nothing from our body and generated at different frequencies by different organs and/or muscles and tissues, and transduce them, through a series of sensors and with appropriate algorithms, into different vital signals.

Specifically, the parameters Soundi detects are:

- Temperature
- Heart rate
- ECG
- Oxygen saturation
- Respiratory rate
- Flow
- Snoring
- Nocturnal posture
- Numeropassi.

Soundi is also able to record environmental parameters in which the individual lives, in particular it detects temperature, relative humidity, pressure, CO2 equivalent, Volatile Organic Compounds (VOC) produced by human breathing (for example CO) and by the environment (for example formaldehyde).

Soundi is a small (diameter of 60 mm and height of 12 mm), lightweight, which is applied with a double-adhesive medical patch on the left hemithorax and can record the parameters over 24 hours for up to 15 consecutive days. Equipped with a rechargeable battery, it is capable of providing continuous measurement of the main physiological parameters.

Soundi is made up of the following components (Figure 1):

1. multi-sensor measuring unit (Figure 2)
2. ignition key

3. a double-adhesive medical plaster.

Figure 1. SOUNDI:1.Measurement unit;2.Ignition key;3.Double-sided medical tape.

[figure not shown]

Figure2. Image of the SOUNDI multisensor measurement unit

Soundi is supplied with the following accessories:

- 1-channel ECG cable
- USB cable to allow charging of the rechargeable battery and connection to the PC
- power supply
- software pcSOUNDIDOC.

The device will be used for full cardiorespiratory monitoring.

Being a wearable device also intended for non-hospitalized patients, SOUNDI is also intended to be used in a home environment.

The SOUNDI device records in internal memory the physiological data of the monitored person. The data is then downloaded, via USB cable, to the PC to be converted into a file with standard edf, the same format as the file returned by the standard polysomnography device.

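### Does the missing thoracic and abdominal respiration signal in the SOUNDI lists undermine the blinded comparison with polysomnography?

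*Protocol*

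**What the plan says.** **Signals.** Section 7 (Study procedures) states that "the following parameters will be acquired with two systems: oro-nasal flow, thoracic and abdominal respirations", then adds snoring, ECG, oxygen saturation and body position. The same section derives the diagnostic indices from both systems, among them central and obstructive AHI. This is done by automatic RemLogic analysis followed by manual correction by a sleep physician.

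**SOUNDI as described.** Section 2.2 gives an open-ended list of what the device measures: "temperature, ECG, ejection fraction, blood pressure, respiratory rate, flow, oxygen saturation, apnea/hypopnea index". Section 3 gives another list, introduced by "Specifically, the parameters Soundi detects are". Its nine items are temperature, heart rate, ECG, oxygen saturation, respiratory rate, flow, snoring, posture and steps. The hardware is a single multi-sensor unit "applied with a double-adhesive medical patch on the left hemithorax", with a key, a plaster, a "1-channel ECG cable", a USB cable, a power supply and software. Section 3 also states: "The device will be used for full cardiorespiratory monitoring". Section 2.1 describes cardiorespiratory polysomnography as the variant in which "the number of parameters is smaller (nasal, thoracic and abdominal respiration, body position, oximetry, ECG".

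**Protection against bias.** SOUNDI data are converted to edf, "the same format as the file returned by the standard polysomnography device". Section 11.4 relies on common software and on a corrector blinded to three things: who the subject is, which device produced the data, and what the other device showed. It refers to the investigator's dossier for further detail.

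**The concern.** Section 7 credits both systems with a signal that no SOUNDI list contains. A single chest unit with a one-channel ECG lead has no obvious abdominal sensor, so a reader may doubt that the signal exists on the SOUNDI side.

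Two consequences would follow if it did not.

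- **Recognition of the device.** A shared file format and shared software do not hide which channels are on the screen. A recording without respiratory effort traces would reveal its source, and device blinding would fail. Every index in the primary comparison passes through the manual correction, and the protocol does not say that uncorrected values are kept. Agreement might then owe something to the corrector as well as to the device.
- **Interpretation of two indices.** Central and obstructive AHI would rest on different information in the two systems, and a reader of those results would need to know it. That effort signals are used to separate the two event types is an assumption here, because the protocol does not say which signals serve that purpose.

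**Working it through.** **1. Match the signals.** Section 7 signals against the section 3 SOUNDI list:

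| Section 7 signal | Named for SOUNDI in section 3? |
|---|---|
| Oro-nasal flow | Yes, as flow |
| Thoracic and abdominal respiration | No |
| Snoring | Yes |
| ECG | Yes |
| Oxygen saturation | Yes |
| Body position | Yes, as posture |

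Five of six match. Section 2.2 adds three outputs to the nine in section 3 (blood pressure, ejection fraction, AHI), giving 9 + 3 = 12 distinct physiological outputs. None is thoracic or abdominal respiration.

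**2. Ask how much the silence proves.** Those three additions show that the section 3 list is not complete even for outputs the protocol names elsewhere. The section 2.2 list is illustrative by its own wording. Both mix derived quantities (heart rate, respiratory rate, steps) with raw signals, so neither is a channel list. Section 3 says that the device obtains different vital signals from its sensors by means of algorithms, so a derived effort trace would need no belt or extra lead. The unit image and block diagram are not reproduced in the text available. Absence from these lists is therefore weak evidence that the signal is absent.

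**3. Look for text the other way.** Section 3 assigns SOUNDI to full cardiorespiratory monitoring. Section 2.1 includes thoracic and abdominal respiration in that kind of study. Section 4 has both systems acquiring the signals simultaneously, and section 7 names the signal for two systems. Together these attribute the signal to SOUNDI without saying how it is obtained.

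**4. Follow the blinding argument.** For the primary comparison to be biased by this route, all of the following must hold:

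- SOUNDI supplies no such trace, or one that looks different.
- The display given to the corrector shows the difference.
- Nothing masks it, in the dossier or in practice.
- Recognising the device changes the scoring.
- The change moves the two sets of indices towards, or away from, each other.

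The document establishes none of these. On the last, the corrector is also blind to the subject and to the paired result, so has no known value to correct towards. A general leaning for or against one device remains possible, but its direction and size are unknown.

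**5. See whether a size can be given.** The plan's own figure reproduces. With CCC 0.60 under H0, 0.81 under H1, one-sided 5% and 90% power, the Fisher z approximation gives ((1.645 + 1.282) / (atanh 0.81 − atanh 0.60))² + 3 = (2.927 / 0.434)² + 3 ≈ 48.5, hence 49 against the stated 50. Power at 50 is about 0.91.

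With equal means and equal variances s², the variance of the differences is 2s²(1 − CCC). Moving from 0.60 to 0.81 therefore needs the SD of the differences to fall by the factor √(0.19 / 0.40) = 0.689, that is by 31%. This describes the distance between the two hypotheses. Nothing in the protocol links it to channel display or to recognition of the device, so it is not an estimate of bias.

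**6. Mark out the reach.** Correction covers 50 × 2 = 100 planned recordings and at least 11 indices: four AHI measures, ODI, three saturation measures, two heart rate measures and at least one position percentage. A missing effort signal as such would bear on two of them, central and obstructive AHI, under the assumption stated above. Section 11.1 assesses agreement parameter by parameter, so weakness in those two would tend to appear in their own CCC and Bland-Altman results.

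**The case for a change.** The strongest case for a change is that the introduction to the section 3 list reads as a specific statement of what SOUNDI detects, so the omission there contradicts section 7. On this view, reader blinding is a design matter that the protocol should secure. The blinding in section 11.4 is asserted without file coding, reading order or channel masking. The remedies are cheap: name the signal, code and randomise the files, and keep the automatic indices so that agreement before correction can be shown beside agreement after it. Once the reading is done, values that were not kept may be hard to recover.

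Part of this stands. The signal is never identified, and a sentence saying whether it is measured or derived would help. It is also true that a common format and common software do not by themselves conceal a difference in channels.

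The rest does not amount to a correction. Coding and ordering of files are ways of carrying out a blinding that the protocol already requires, and section 11.4 points to the dossier for such detail. Agreement on uncorrected indices is a sensitivity analysis of a kind commonly left to a statistical analysis plan, which is not at hand. Its reading would be ambiguous too, because manual correction also removes software errors, so a gap between the two analyses would not show bias.

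**Conclusion.** No change to the plan follows. The mismatch between section 7 and the SOUNDI lists is genuine but small: one signal of six is not named. The protocol's general statements still attribute that signal to the device, so this is incomplete description and not a demonstrated contradiction. The blinding rule in section 11.4, followed as written, is sound. The document does not show that it fails or that agreement is biased, and no size can be put on such a bias.

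This rests on two assumptions: that SOUNDI supplies a measured or derived respiratory effort trace, as section 7 and the stated intended use imply, and that the corrector is kept blind to subject, device and paired result, as section 11.4 requires. If the first proved false, the central and obstructive AHI results would need a note on interpretation, and device blinding would have to be described as partial if the displayed channels then differed.

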7.1 Compliance with procedures

All tests without artifacts invalidating the interpretation of one or more signals acquired for at least 4 hours of sleep will be considered valid.

7.2 Follow up

Unless particular problems are reported to the patient (adverse events or effects related to the use of the device in the study) which will be followed by specific assessments, a follow-up will not be necessary.

8. Duration of the study

The expected duration of enrollment of all subjects is approximately 6 months.

The expected duration of the study for the subject is a maximum of 24 hours.

The start of the study is defined by the date of signing the consent of the first patient and the end of the study by the last data analysis of the last patient.

The overall duration of the study will be 1 year.

8.1 Interruption and withdrawal of subjects from the clinical investigation

Each patient is free to withdraw from the study at any time or his participation may be interrupted by decision of the trial for safety, behavioral or reasons administrative.

Reasons for discontinuing a patient's participation in the study may include:

- withdrawal of consent by the patient
- the change in the patient's clinical-functional conditions that do not allow participation
- lack of adherence to the procedures required by the study protocol on the part of the patient
- an adverse event (related or unrelated to the study device) which, in the opinion of the Principal Investigator, does not allow the continuation of the study itself.

If the study is interrupted for any of the reasons listed above, the measurements taken will not be considered in the statistical analysis.

The reasons for stopping the study will be recorded in CRF.

Unless particular problems are reported to the patient (adverse events or effects related to the use of the device in the study) which will be followed by specific assessments, a follow-up will not be necessary.

Patients excluded from the study and who cannot obtain the data required by the study protocol will be replaced to reach the required number.

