11.2 Securityanalysis

The safety analyzes will be carried out on all patients to whom the Sound device and the polysomnography device have been applied, regardless of the validity of the data collected.

In general, safety analyzes will be descriptive in nature. The frequency, severity, severity and causal relationship of adverse events will be tabulated.

Both the number and percentage of events and patients experiencing an event will be presented. Additionally, adverse events that led to study suspension and device defects reported.

Sample size.

A sample of 50 analyzable patients will guarantee a power of 90% in determining six values of the parameters detected with the SOUND I method are in agreement with those measured by polysomnography. The estimate was made considering: i) a z-head and a tail with a significance level of 5%; ii) a value of the CCCparia 0.60 below H0; iii) a value of the CCCparia 0.81 below H1 . Sample sizing was performed using PASS2021(PowerAnalysisandSampleSizeSoftware(2021).NCSS,LLC.Kaysville,Utah,USA).

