11.3 Analysis set

Efficacy analyzes will be carried out on all patients who have completed the evaluation and whose data will be considered evaluable.

The following will be excluded from the statistical evaluation:

- all measurements lasting less than 4 ha cause the malfunction/
- malposition of the device
- data obtained from measurements of patients excluded from the study.

The safety analyzes will be carried out on all patients to whom the Soundi device and the polysomnography device (safety population) have been applied, regardless of the validity of the data collected.

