11.4 Systematic errors - bias

Any distortions will be prevented by deriving the indices used for the diagnosis of respiratory and sleep disorders from both methods (Polysomnigraph and Soundi) using the same automatic analysis software (RemLogic).

This will then be followed by manual correction by the operator expert in sleep medicine who is blind to: the identity of the subject under examination, the device with which the data are obtained and the outcome of the same parameters obtained with the comparison device.

To document the patient selection bias, all reasons for non-participation in the study will be recorded on a specific form (Screening Log) and considered in the subsequent statistical analysis.

Impairment of the results or interpretation of the results may be caused by malposition or malfunction of the device.

Specifically, a check of all the sensors when the device is started was included in the design phase. In the event of a malfunction of one of them, it is signaled by a flashing red LED. In this case the measurement can be repeated with another device supplied.

In the event of bad positioning, the measurement results may be compromised and the signal may be incomparable with that acquired by the polysomnography machine. In this last case the measurement is unusable for the study and the patient data will not be included in the effectiveness analysis.

How to minimize these biases is further detailed in the dossier for the investigator.

12.Medical device

It is planned to use 2 experimental devices (SOUNDI system, Biocubica) and 1 product

comparison (polysomnograph, Embletta, Natus).

The experimental SOUNDI devices will be supplied by the Promoter and will be identified by a batch number and a serial number.

The Investigator will be responsible for keeping track of the experimental devices from their delivery to the center until they are returned to the Sponsor at the end of the study.

The devices will be stored centrally in a secure location where only authorized personnel can access them and at a temperature between -25°C and +70°C and a relative humidity of less than 93%, as indicated by the manufacturer, until delivery to the patient.

If a device is lost or damaged, the Investigator will notify it immediately to the Promoter.

The polysomnograph (Embletta, Natus) is already present at the center as it is used for clinical practice.

13. Ethical and regulatory aspects

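### Agreement is assessed only on usable nights, and no effectiveness measure shows how often SOUNDI, compared with the polysomnograph, fails to give the diagnostic indices

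*Protocol*

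**What the plan says.** Protocol 5.1 sets the primary objective as SOUNDI's effectiveness in detecting the parameters needed to diagnose OSA. Protocol 9.1 makes the primary endpoint equivalence of that detection with polysomnography. Protocol 11.1 assesses it, parameter by parameter, with the Bland-Altman plot and the CCC.

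The rules on who enters that analysis are spread over several sections:

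- **11.3, analysis set:** "Efficacy analyzes will be carried out on all patients who have completed the evaluation and whose data will be considered evaluable". Recordings shorter than 4 hours because of malfunction or malposition are excluded.
- **11.4, malposition:** a badly positioned device may give a signal that cannot be compared with the polysomnograph's. That patient is left out of the effectiveness analysis.
- **11.4, malfunction:** a sensor fault found by the start-up check is signalled by a red LED. "In this case the measurement can be repeated with another device supplied".
- **8.1, replacement:** patients excluded from the study and "who cannot obtain the data required by the study protocol will be replaced to reach the required number".
- **Sample-size text, placed under 11.2:** "A sample of 50 analyzable patients will guarantee a power of 90" per cent.

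The only secondary effectiveness endpoint (9.2) is patient satisfaction. Device defects are reported descriptively under safety (11.2), in the population fitted with both systems, whether or not the recording was valid.

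**The concern.** A night on which SOUNDI was worn but gave no usable AHI or oximetry is a failure at the task named in the primary objective. Such a night contributes no pair to the CCC or the Bland-Altman plot, and the target of 50 is then made up with other patients. A device that never loses a night and one that loses many would both be judged on 50 usable pairs.

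The protocol's case for SOUNDI is easier access to diagnosis, fewer hospital visits and use at home (2.2 and 3). A lost night works against each of these. A reader of the effectiveness result would want to know how often it happens, and whether it happens more often than with the polysomnograph worn on the same night.

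**Working it through.** **1. Inputs for the plan's own figure (sample-size text under 11.2).** The CCC is "a value of the CCCparia 0.60 below H0" and "a value of the CCCparia 0.81 below H1". The test is described as "a z-head and a tail with a significance level of 5" per cent, which in this translation I read as a one-tailed z test at 5%. Power is 90%, with 50 analysable patients.

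**2. Reproducing it.** On Fisher's z scale the effect is d = atanh(0.81) − atanh(0.60) = 1.1270 − 0.6931 = 0.4339.

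n = ((z₀.₉₅ + z₀.₉₀)/d)² + k, with k = 2 (Lin's variance) or k = 3 (Fisher's).

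- ((1.645 + 1.282)/0.4339)² = 45.5
- k = 2: 47.5, so 48 patients. k = 3: 48.5, so 49 patients.
- Power at n = 50 is Φ(d·√(50 − k) − 1.645) = 91.3% (k = 2) or 90.8% (k = 3). A simulation of bivariate normal pairs with equal means and variances gave 90.3%.
- A two-sided 5% test would need 58 to 59 patients and would have 84 to 85% power at 50. The one-tailed reading is therefore the one that fits.

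The stated 50 patients and 90% power reproduce. The calculation is conditional on 50 analysable pairs and contains no term for lost nights.

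**3. What the CCC analysis sees as losses rise.** The protocol gives no failure rate, so the share f of fitted patients without a usable night is assumed. Patients fitted to reach 50 usable = 50/(1 − f), rounded up. Intervals are exact (Clopper-Pearson).

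| Assumed f | Patients fitted | Pairs in CCC analysis | Usable share of fitted (95% CI) |
|---|---|---|---|
| 5% | 53 | 50 | 94% (84-99%) |
| 10% | 56 | 50 | 89% (78-96%) |
| 20% | 63 | 50 | 79% (67-89%) |
| 30% | 72 | 50 | 69% (57-80%) |

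The third column does not move. The fourth is the quantity that no effectiveness analysis reports.

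**4. The same point as a failure rate (also assumed, all losses attributed to SOUNDI).** 10/60 = 16.7% (8.3-28.5%). 5/55 = 9.1% (3.0-20.0%).

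**5. Does anything else in the protocol supply this rate?**

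- Safety (11.2): defects are reported. The definition in 10.2 covers deficiencies of reliability or performance, malfunction and errors in use, but it concerns the device under investigation, so the polysomnograph has no equivalent. A count of defects is also not the share of nights that gave the indices.
- Screening Log (6.1 and 11.4): it records reasons for not taking part, not lost nights.
- Enrolment (6.1): "The study involves the enrollment of 50 patients belonging to a single Italian centre". This makes no allowance for unusable nights, so reaching 50 analysable patients depends on replacement whenever any are lost.

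**The case against.** The other side has good points, and several limit how far the criticism goes.

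*Failures are not hidden.* A reader might infer that lost nights disappear from the report. The documents do not support that. The defect definition can take in signal loss and staff malpositioning, and the safety population gives a denominator. The gap between the safety population and the effectiveness set would show the total lost. What remains is that this total is not split by cause or by system, and stays outside the effectiveness conclusion.

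*Section 8.1 is about withdrawal.* None of its listed reasons is device failure, and in translation the replacement sentence can be read as requiring both exclusion and missing data. It is therefore too strong to say that 8.1 plainly orders replacement after every failed SOUNDI night. The point does not depend on it: 11.3 and 11.4 remove the recordings on either reading, and a target of 50 analysable patients implies filling up.

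*Not every loss is SOUNDI's.* The patient or the polysomnograph can also cause one. The excluded share must not be read as a SOUNDI failure rate, which is why causes need to be recorded.

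*The LED swap is not a lost night.* It follows a check at start-up, and a faulty unit may be replaced before anything is recorded. Scoring each swap as a failed night would be unfair to the device.

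*Agreement methods need pairs, and extra tables belong in the SAP.* The first part is true, and the conditioning is stated openly in 11.3. But the endpoints, the analysis set and the replacement rule are all fixed in the protocol. Whether failure to obtain the indices counts towards effectiveness is decided there.

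**Conclusion.** The point holds as a limitation of what the effectiveness analysis can conclude. The agreement results will describe SOUNDI on nights that worked, while the objective concerns detecting the parameters at all. No effectiveness measure covers the difference, and none compares the two systems on it.

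Its size cannot be computed, because the protocol gives no expected failure rate. The 17% and 9% above are illustrations, not predictions, and nothing in the document suggests that SOUNDI fails often. The sample size is not in error: 50 patients and 90% power reproduce, and the CCC analysis is valid for what it conditions on. This is an inexpensive improvement that should be made.

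**What to change.** Keep replacement and the CCC analysis as they are. Add to 9.2 and 11.1:

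- **Endpoint:** the proportion of the safety population (all patients fitted with both systems) whose overnight recording meets the 4-hour, artifact-free rule of 7.1 and yields the indices. Section 7.1 is written for a test as a whole, so state that it is applied to each system's recording separately.
- **Reporting:** SOUNDI and the polysomnograph separately, each with an exact 95% CI, and the paired difference between them.
- **Causes:** each loss classified as device malfunction, malposition, polysomnograph or patient, taken from the CRF and the recordings.
- **Swaps and repeats:** start-up swaps flagged by the LED shown as a separate count. Count as a SOUNDI failure only a night that was recorded and was unusable or had to be repeated.
- **Wording of the conclusion:** the CCC result stated as conditional on a valid night, with this rate beside it.

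The cost is one extra table from data already held, and possibly a less favourable headline. No added patients or procedures are needed.
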